## OBJECTIVES/AIMS

---

The objective of this study is to: a) adapt the intervention for Latinx immigrants (*Immigrant Wellbeing Project; IWP*); b) integrate *IWP* into existing efforts at four community partner organizations; and c) elucidate new understandings of partnership and intervention processes that lead to sustainable multilevel changes and the reduction of mental health disparities and related social inequities.

**Aim 1.** Conduct an in-depth study of the mental health needs, stressors, current political/economic/social context, and local solutions as experienced by 24 Latinx recent and non-recent immigrants and their families residing in Bernalillo County New Mexico and contextualized by staff at four community partner organizations.

**Aim 2.** Building on the data from Aim 1, use a CBPR approach to adapt the intervention model (*IWP*) and integrate it within existing service delivery and social change efforts at four community partner organizations.

**Aim 3.** Using a mixed methods longitudinal design, investigate the feasibility and acceptability of the adapted community-based mental health intervention and test the quality of the CBPR partnership and impact of the intervention on mental health problems and protective factors among 90 Latinx immigrants and on organizational and government changes in policies and practices impacting

immigrant mental health.

**3.1** The *IWP* and collaborative adaptation/integration process will be feasible and acceptable and will serve as a model for implementing and studying multilevel, community-based intervention efforts.

**3.2** *IWP* participants' psychological distress will decrease significantly over time.

**3.3** *IWP* participants' protective factors (access to resources, English proficiency, environmental mastery, social support) will increase significantly over time.

**3.4** Lower levels of psychological distress will be mediated by the protective factors.

**3.5** Qualitative data will document changes in organizational and governmental policies and practices and the context of implementation at each site, explore other impacts, and inform interpretation of quantitative data.

**3.6** Quality of CBPR partnership at each site will be related to policy/practice changes and health outcomes.

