### **II. Participant Enrollment**

24 Latinx immigrant adult participants will be enrolled in Aim 1.

90 Latinx immigrant adult participants will be enrolled in Aim 3 to participate in the intervention and 4 interviews each.

6 organizational staff will be enrolled in Aim 3 to complete 2 qualitative interviews each.

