### **III. Recruitment and Screening Procedures**

Recruitment will occur in coordination with the four community partner organizations (Centro Sávila, Encuentro, New Mexico Dream Team, and New Mexico Immigrant Law Center) and will be conducted by the Research Coordinator and RA [name]. Organizations will identify potential participants among those whom they are serving. We do not anticipate using flyers or recruitment materials, but if our partner organizations think that a flyer would be helpful, we will create it with feedback from our partner organizations and submit it to the IRB for approval prior to conducting recruitment. The Research Coordinator and/or [name] will meet in-person with potential participants who are referred by community partner organizations. The study staff member will ensure that the potential participant is a resident of Bernalillo County and an immigrant from Mexico. If the potential participant does not meet these eligibility requirements, he/she will not be enrolled in the study. No data will be collected from potential participants who do not meet eligibility requirements. No data will be collected from potential participants who do not meet eligibility requirements. Exclusion will be based on review of interview data by the PI and [name], therapist and director of Centro Sávila. Excluded adults (except those with cognitive functioning issues already being addressed or those already in treatment) will be referred immediately for individual treatment. Data collected from any excluded adults will be destroyed.

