**Aim 3:** Aim 3 involves an intervention and 4 individual interviews with each participant. The Immigrant Well-being Project (IWP) Intervention Model is a 6-month intervention with two main components: 1) Learning Circles. Learning Circles (LCs) occur once per week for six months (total of 24 LCs). Each meeting is two hours and includes immigrants and undergraduate paraprofessionals. LCs have two parts: cultural exchange and one-on-one learning. Cultural exchange occurs for the first hour and is facilitated together by one undergrad and one immigrant who choose the topic. To enable all participants to share in the discussion, interpreters are present. Cultural exchange provides a forum for immigrants and undergrads to learn from each other, share ideas, develop plans for collective action, and realize the important contributions they are capable of making. The second component of the LCs is one-on-one learning. For the last hour, immigrants and undergrads work in pairs. During one-on-one time, immigrants direct their own learning (e.g. English, job applications). 2) Advocacy. Advocacy begins after the first two weeks of LCs. For the remaining 5½ months of *IWP*, undergrads spend an additional 4-6 hours each week (outside of the LCs) with their immigrant partner(s) to engage in advocacy together around any issues the immigrant(s) would like to address. They follow a 4-phase process (assessment, implementation, monitoring, and secondary implementation) for each unmet need or goal. Undergrads also work to transfer advocacy skills to their partner, through shared engagement in advocacy, modeling, and role plays. The *IWP* employs a holistic approach that integrates advocacy and learning to address multiple needs of immigrants (i.e., English proficiency, access to resources, understanding of their environment, social support, valued social roles). However, rather than emphasizing only what immigrants need to learn to survive in the U.S., the *IWP* focuses on

**mutual learning**, through which immigrants both learn from and teach people born in the U.S.

Quantitative interview procedure. Each participant will complete 4 quantitative interviews: pre, mid (~3 months after pre), post (~6 months after pre), and follow-up (14 months after pre). The 1-1½ hour

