## VI. *Study Timelines*

The study is funded for almost 5 years (9/23/18-6/30/23). Aim 1 data collection will occur during Year 1 (January-March 2018). Aim 3 intervention and data collection will be implemented in three waves (months 15-20, 27-32, 39-44). Each wave will occur at a different community partner organization and will be adapted and integrated into existing activities and services in different ways, with the goal of creating sustainable, community-level changes by building upon community mobilization/organizing/social change efforts and social networks that are essential components of achieving sustainable, community-level changes. Data collection will end by October 2022.

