## II. Benefits

The risks of this project are reasonable when compared to the expected benefits to the participants and others. The potential benefits of this study are great. Immigrant adults will have the opportunity to learn, work together to address community issues, increase their social support, and improve their access to community resources. Based on the previous studies of the intervention model, it is expected that the intervention will reduce distress and increase protective factors among participants. Latinx immigrants in New Mexico and throughout the United States continue to struggle and experience high rates of psychological distress. Thus, this intervention has significant potential for improving the lives of these groups. Furthermore, if the intervention and the adaptation process demonstrate feasibility, acceptability, appropriateness, and effectiveness, the intervention and adaptation process can be disseminated throughout the United States to improve the lives of other immigrants and marginalized populations.

The knowledge that will be acquired from this study will further our understanding of community-based mental health interventions for marginalized populations that address social-structural determinants of mental health and will contribute to our ability to reduce the high rates and disproportionate burden of mental illness experienced by socioeconomically disadvantaged Latinx immigrants in the United States. As stated previously, this knowledge has important implications for Latinx immigrants, as well as all other immigrants and refugees who resettle in the United States. In addition, the knowledge generated from this study is important in furthering the fields of research of immigrant mental health and health disparities. It is particularly important to design, implement, and evaluate innovative, multilevel mental health interventions for immigrants that address the social and structural determinants of health because limited research exists in this area. There are also specific benefits to communities and broader society in terms of the data that are collected, because the data can further our understanding of the experiences of Latinx immigrant adults and can demonstrate that universities in partnership with communities can provide evidence-based interventions. Thus, the potential benefits to participants and other immigrants and the knowledge gained outweigh the slightly more than minimal risks to study participants.

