***Hypothesis 3.3*** *IWP participants’ protective factors (access to resources, English proficiency, environmental mastery, social support) will increase significantly over time.* Growth curve modeling will be implemented using hierarchical linear modeling (HLM). Analyses will proceed sequentially beginning with baseline ‘intercept-only’ models, then testing fully parameterized model (see Goodkind, et al., 2012 for detailed description of analytic method). If this iterative process identifies that the best fitting model includes significant random effects corresponding to the significant fixed effects (i.e., that there is significant variability in intercepts and/or slopes), we will attempt to model it using level-2 predictors. Level-2 predictors to be tested as potential moderators will include sex, age, length of time in the U.S., and intervention hours, which will allow us to identify relevant individual difference variables (e.g., age) that may predict response to the intervention and to test whether intervention dosage predicts differential change (a finding that would strengthen the inference of treatment effects). Calculating effect sizes for multilevel models is complex; because our focus will be the effect of the intervention over time, we will examine the percentage of variance explained (PVE) by the addition of time to each model by comparing the PVE of the best fit Level 1 model to the Level 1 intercept-only model.

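### Aim 3 measures change over time in one group that all receives IWP, but the plan words that change as the effect and impact of the intervention

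*Combined protocol and SAP*

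**What the plan says.** II. Participant Enrollment puts everyone in the intervention: "90 Latinx immigrant adult participants will be enrolled in Aim 3 to participate in the intervention and 4 interviews each". V. Data Collection Procedures sets one interview before IWP and three after it starts, at about 3, about 6 and 14 months. Neither section mentions a control group, a wait-list or a second baseline.

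III. Recruitment and Screening Procedures draws participants from existing clients: "Organizations will identify potential participants among those whom they are serving". VII. Study Location(s) lists what those clients can receive, including outpatient mental health care, case management, insurance enrollment help, legal services and education. VI. Study Timelines adds: "Each wave will occur at a different community partner organization and will be adapted and integrated into existing activities and services in different ways".

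The hypotheses are modest. Hypotheses 3.2 and 3.3 say that distress will fall and protective factors will rise over time. The causal wording lies around them, in four places:

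- Aim 3 (OBJECTIVES/AIMS) is to test the "impact of the intervention on mental health problems and protective factors among 90 Latinx immigrants".
- The effect-size passage under Hypothesis 3.3 (STUDY DATA, II. Data Analysis/Statistical Considerations) chooses the percentage of variance explained (PVE) by adding time, "because our focus will be the effect of the intervention over time".
- The opening paragraphs of the same section plan complier average causal effects.
- Hypothesis 3.4 describes its models as examining how the intervention is effective.

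The plan has one partial safeguard. Under Hypothesis 3.3, intervention hours are a possible level-2 moderator, and a dose relation is said to support a treatment inference.

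**The concern.** A significant time term answers whether participants changed. It does not answer whether IWP changed them. The documents themselves supply other reasons for change:

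- **Concurrent services.** The partner organizations work on distress and access to resources, which are also study outcomes, and they do so over the same months.
- **Secular change.** The background section gives policy and political climate a critical role in this population's mental health. The three waves run between months 15 and 44. Neither wave nor site is among the listed level-2 predictors.
- **Repeat testing and longer residence.** Each participant has four interviews over 14 months. English scores in particular could rise from practice or from more time in the country.
- **Natural course.** No untreated interval is observed.

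These influences need not all favour IWP. A worsening climate could hide a real benefit. In either direction, the main quantitative conclusion of Aim 3 would be worded as causal without a design that can support it.

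**Working it through.** **1. The plan's own figure.** The sample size is 90. The only supporting arithmetic is the count of partner interviews in V. Data Collection Procedures: 30 pairs × 3 waves = 90. No alpha, power, effect size, SD or dropout rate is stated, so 90 cannot be reproduced as a power calculation.

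**2. What the model can identify.** Write the mean change at time t as b(t) + θ(t), where b is background change and θ is the IWP effect. The growth model has an intercept, time, and possible moderators (sex, age, time in the U.S., intervention hours). Everyone is treated from the start and has one pre-intervention value, so only the sum b + θ is estimable. The PVE from adding time describes that sum.

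**3. How easily background change alone becomes significant.** These inputs are assumptions, not in the documents: θ = 0, two-sided alpha 0.05, a background improvement of d SD, pre-post correlation r, equal SDs, and a one-group pre-post test with n = 90. SE = √(2(1 − r)/90). The probability of significance comes from the noncentral t distribution with 89 df and noncentrality d/SE.

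| r | SE (SD units) | d = 0.2: d/SE | significant | d = 0.3: d/SE | significant |
|---|---|---|---|---|---|
| 0.5 | 0.105 | 1.90 | 46.7% | 2.85 | 80.4% |
| 0.6 | 0.094 | 2.12 | 55.5% | 3.18 | 88.2% |
| 0.7 | 0.082 | 2.45 | 67.8% | 3.67 | 95.3% |

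If 72 remain (an assumed 20% loss), the ranges are 38.8% to 58.0% at 0.2 SD and 70.9% to 90.0% at 0.3 SD.

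**4. The same check on a four-point slope.** This used 4,000 simulated studies with interviews at 0, 3, 6 and 14 months, a random intercept with intraclass correlation 0.6, and no IWP effect. With no drift, 4.8% were significant, as expected.

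- Improvement reaches 0.2 SD at 6 months and then stays level: 53% significant, mean PVE 1.5%.
- Improvement reaches 0.3 SD at 6 months and then stays level: 85% significant, mean PVE 3.3%.
- Improvement of 0.1 SD per 6 months continues throughout (0.1 × 14/6 = 0.23 SD by 14 months): 74% significant, mean PVE 2.5%.

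This is a simpler model than the planned one. True variation in slopes between people would lower these rates.

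**5. Regression to the mean, taken separately.** If clients enrol s SD above their usual level, the expected fall is s(1 − r). For s = 0.25 to 0.75 and r = 0.8 to 0.6, that is 0.25 × 0.2 = 0.05 to 0.75 × 0.4 = 0.30 SD. Excluding the most distressed fraction q at baseline works the other way. The baseline mean drops by φ(c)/(1 − q), where c is the normal cut-off, and the later rise is that drop times (1 − r). For q = 2% and r = 0.8 the rise is 0.049 × 0.2 = 0.01 SD. For q = 10% and r = 0.6 it is 0.195 × 0.4 = 0.08 SD. The documents fix neither s nor q, so even the sign is open.

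**The case against.** The strongest reply is that the plan does not rest on the time term alone. The hypotheses promise only change, the dosage test looks for supporting evidence, the mediation models examine timing, and qualitative interviews explore how participants see the change. This is fair, and it confines the fault to wording and inference. It does not remove it. Hours attended are not randomised and may follow improvement or engagement. The moderators are modelled only if random effects prove significant. Neither the mediation models nor the interviews supply a course without IWP.

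Three stronger readings are tempting but unsupported:

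- *A reader might infer that people are recruited at their worst, so that distress must fall by regression to the mean.* The documents do not say that clients enter when need is acute. I. Potential Risks describes IWP as open to all interested immigrants, so there is no distress threshold. The eligibility section excludes people with very severe illness, and recruitment bases exclusion on interview data. Regression to the mean is possible through help-seeking, but it is the weakest mechanism.
- *A reader might infer that a significant slope triggers national dissemination.* II. Benefits says only: "if the intervention and the adaptation process demonstrate feasibility, acceptability, appropriateness, and effectiveness, the intervention and adaptation process can be disseminated". It names no test and sets no criterion.
- *A reader might look to the staggered waves for a control.* All pre interviews are of newly enrolled clients, so their means can show only calendar drift, and each wave is at a different organization. At 30 per wave, the SE of a difference between two pre means is √(2/30) = 0.26 SD, a 95% half-width of about 0.51 SD. Counting months from the funding start, a wave 3 follow-up at month 39 + 14 = 53 falls in about early 2023, after the stated October 2022 end of data collection.

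**Conclusion.** The concern holds as a mismatch between design and wording, and it should be fixed. The single-group design is a legitimate choice for a study of feasibility, acceptability and change, and Hypotheses 3.2 and 3.3 can be tested as written. What the design cannot support is calling the time effect the effect, impact or effectiveness of IWP, or estimating a complier average causal effect when no comparison arm is described. Concurrent services and secular change are the best-supported rival explanations.

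The size rests wholly on assumptions. With 90 participants and no IWP effect, a modest background improvement of 0.2 to 0.3 SD would be significant in roughly half to nearly all studies, depending on the correlation. The documents do not say whether background change of that size, or in that direction, will occur. The figures show only that a significant time term would be weak evidence for IWP.

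**What to change.** 1. In Aim 3, in the effect-size text under Hypothesis 3.3 and in the opening of Hypothesis 3.4, replace the terms impact, effect of the intervention and intervention effectiveness with change over time during and after IWP. Label the PVE as variance explained by time.
2. In the opening paragraphs of the analysis section, drop the complier average causal effect, or restate it as a non-causal association between dose and change.
3. State that a significant time term alone will not be reported as evidence that IWP is effective, and that this applies to the dissemination statement in II. Benefits. Name concurrent services, secular change, repeat testing and natural course as alternative explanations.
4. Optionally, add the mental health service use items already in Table 2 as a predictor in the growth model and present the result as descriptive. The items cover neither legal nor educational services, and service use after enrolment may itself result from IWP.

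The wave pre-interview means should not be offered as a remedy.

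The cost is a few sentences and, if item 4 is taken up, one further analysis of data already planned. No hypothesis, sample size or visit changes. The real price is a less favourable claim.

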***Hypothesis 3.4*** *Lower levels of psychological distress will be mediated by increased access to resources, English proficiency, environmental mastery, and social support.* The mechanisms of intervention effectiveness will be examined through structural equation modeling (SEM), which will allow modeling of mediation pathways linking intervention components to primary outcomes via effects on protective factors. Multigroup SEM will provide tests of mediation effects. Latent change and latent trajectory modeling will be used to assess longitudinal mediation effects, including the effects of change from baseline to mid- and post-intervention on protective factors (e.g., access to resources, English proficiency, social support, environmental mastery) on subsequent change in primary outcomes (e.g., PTSD, depression, and culturally-specific distress symptoms over time) and parallel- or lagged-process links between change trajectories on protective factors and primary outcomes over time. Mplus software will be used for these analyses, due to its flexible estimation capabilities and ability to test specific mediation effects.

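### Hypothesis 3.4: with one exposed group receiving both components, the SEM can show associations between changes but cannot show mechanisms of intervention effectiveness

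*Combined protocol and SAP*

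**What the plan says.** The Objectives/Aims section states 3.4 without mentioning components: "Lower levels of psychological distress will be mediated by the protective factors". The analysis text for Hypothesis 3.4, under Data Analysis/Statistical Considerations, goes further. It opens with "The mechanisms of intervention effectiveness will be examined through structural equation modeling (SEM") and says that this is an approach "which will allow modeling of mediation pathways linking intervention components to primary outcomes via effects on protective factors". It then names multigroup SEM as the test of mediation, without saying which groups or which exposure variable. It also lists latent change and latent trajectory models. Some of these are time-ordered, with change in protective factors preceding change in distress. Others are parallel-process, with both changes measured over the same period.

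On design, Participant Enrollment says "90 Latinx immigrant adult participants will be enrolled in Aim 3 to participate in the intervention and 4 interviews each". Data Collection Procedures describes what "is a 6-month intervention with two main components". The components are Learning Circles ("Learning Circles (LCs) occur once per week for six months (total of 24 LCs")) and advocacy, in which "undergrads spend an additional 4-6 hours each week (outside of the LCs) with their immigrant partner(s"). The related hypothesis 3.2 is a statement about change in the exposed group only: "participants' psychological distress will decrease significantly over time".

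**The concern.** The analysis text promises a three-link chain: intervention component, then protective factor, then distress. The first link needs variation in receipt of the intervention or its components, and the design assigns none. If the section is followed as written, the exposure and the groups would have to be chosen at analysis. An association between two sets of changes could then be reported as the way IWP works.

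The parallel-process option is the most exposed to this. A legal resolution or a new job during the same months could improve both protective factors and distress. General mood could do the same for the self-reported measures. The result would then look like mediation even if IWP had no effect. The Benefits section links demonstrated effectiveness to dissemination across the United States, so a mechanism claim could carry weight beyond this study.

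**Working it through.** The plan gives no power, effect-size or sample-size figure for 3.4, so there is no stated result to reproduce. The one related sum, 30 pairs × 3 waves = 90 partner interviews, is correct.

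**1. Is the path from receipt to protective factor identified?** All 90 are enrolled to receive the programme. Code receipt of Learning Circles as 1 and receipt of advocacy as 1 for everyone. Each indicator has variance 0, and the matrix (intercept, Learning Circles, advocacy) has rank 1 of 3. Neither a receipt effect nor a component effect is identified at any sample size.

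**2. Does the staggered start help?** Study Timelines gives three waves at different organizations, all exposed. Each participant's interviews run from their own pre-interview, so later waves supply no repeated unexposed measurements.

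**3. Does intervention dose help?** The text for Hypothesis 3.3 lists individual intervention hours as a level-2 predictor. Planned exposure is:
- Learning Circles: 24 × 2 h = 48 h.
- Advocacy, taking 24 − 2 = 22 weeks: 22 × 4 = 88 h to 22 × 6 = 132 h.
- Total: 136 to 180 h, before any missed sessions.

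Hours can therefore vary. With hypothetical hours by component the design matrix has rank 3 of 3, so a dose path can be fitted. It would be observational, because attendance is self-selected. The plan names hours as one total and does not name them for 3.4. Smallest detectable correlation, r = tanh((1.96 + 0.84)/√(n − 3)), assuming two-sided 5% and 80% power:
- n = 90: 0.29
- n = 72 (20% loss): 0.33
- n = 63 (30% loss): 0.35

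**4. Does multigroup SEM help?** It could be run by sex or by wave/site. All groups are exposed, so it would compare protective-factor-to-distress paths between groups, which is moderation. With 30 per wave, two groups must differ by about (1.96 + 0.84) × √(2/27) = 0.76 on the Fisher-z scale. That is roughly a correlation of 0 against one of 0.64, since tanh(0.76) ≈ 0.64.

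**5. What would a shared cause do to the parallel-process model?** Assume that the two slopes correlate at r only through shared causes, and treat slopes as observed. Let z = atanh(r) × √(n − 3). The rejection probability at two-sided 5% is Φ(z − 1.96) + Φ(−z − 1.96).

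| Assumed r | n | z | Probability significant |
|---|---|---|---|
| 0.1 | 90 | 0.94 | about 15% |
| 0.2 | 90 | 1.89 | about 47% |
| 0.3 | 90 | 2.89 | about 82% |
| 0.4 | 90 | 3.95 | about 98% |
| 0.2 | 63 | 1.57 | about 35% |

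This is ordinary power to detect a correlation that exists for reasons other than the intervention.

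**6. Could mean change over time stand in for the first link?** It can be fitted but is confounded with time. A simulation assumed no intervention effect, a 0.4 SD secular rise in the protective factor and a slope of −0.4 on distress. Both links were significant in about 93% of 2,000 trials of n = 90.

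**The case against.** A reader might infer that the path from intervention to protective factor cannot be estimated in any form. The documents do not support that. Intervention hours are planned as a predictor of change, including change in the protective factors under 3.3, and the plan also intends to characterise people who receive a lower dose. An observational dose path is therefore available, although it is confounded and not specified for 3.4.

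A reader might also infer that no groups exist for a multigroup model. Sex and three waves at different organizations are available, and the reference attached to multigroup SEM is, by its title, about combining moderation with mediation. The fault is that the groups are unnamed and the stated purpose does not match what such groups can test.

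Four further points stand:
- The time-ordered models are already in the plan, and the aim as worded does not mention components.
- English proficiency, one of the four protective factors, is measured by a skills test, so mood affecting self-reports does not explain every possible association.
- The percentages depend on assumed correlations for which the documents give no basis. They apply to the parallel-process model only, and they should not be read as this study's false-positive rate.
- The Hypothesis 3.3 text claims only that a dosage finding would strengthen inference, which shows some awareness of the limits.

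None of this supplies the missing contrast. Hours do not measure the effect of receiving IWP, and subgroup comparisons do not test mediation of an intervention effect.

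**Conclusion.** The concern holds, within limits, and should be fixed before analysis. That the effect of receiving IWP or either component is not identified follows from the design alone and needs no numerical assumption. The plan therefore cannot support a conclusion about mechanisms of effectiveness or about component pathways. It can support associations between changes and, if specified, an observational dose association. The size of the risk in the parallel-process models is illustrative: about 15% to 98% significant for assumed shared-cause correlations of 0.1 to 0.4, with n = 90, no attrition and slopes treated as observed. Attrition lowers the figures, as the n = 63 row shows. The defect is confined to what 3.4 may conclude and to unspecified elements of its analysis. It does not make the 3.4 models unusable.

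**What to change.** In Objectives/Aims and in the Hypothesis 3.4 text:

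- Restate 3.4 as: *earlier gains in protective factors will predict later reductions in distress among IWP participants*.
- Make the time-ordered models already listed the test of 3.4. Pre-to-mid change in protective factors predicts mid-to-post change in distress, adjusted for distress at mid. Pre-to-post change predicts post-to-follow-up change in distress, adjusted for distress at post.
- Label the parallel-process models exploratory.
- Either drop the component pathway or define it as observational dose, using intervention hours, by component if they are recorded that way.
- Present multigroup SEM only as a moderation analysis, with the groups named in advance.
- Report all 3.4 results as associations, and state that lagging reduces shared-cause bias but does not remove it.

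The cost is wording in two places and a weaker claim for 3.4. The core change needs no new data, since the time-ordered models and the four interviews are already planned. Hours by component would be needed only if that path is kept.
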